[Part 2 of 2 of the document. The other parts are not shown.]

Therapy	Time period
A change in dose of methotrexate or other DMARD.	12 weeks prior to screening until after the follow up visit (Day 112)
Greater than 10mg/day oral prednisolone (or equivalent glucocorticoid) or a change in dose of corticosteroid.	4 weeks prior to screening until after the follow up visit (Day 112)
Intramuscular glucocorticoids (e.g., methylprednisolone ≤120 mg/month)	4 weeks prior to screening until after the follow up visit (Day 112)
Intra-articular corticosteroid injections	6 weeks prior to screening and until after the follow up visit (Day 112).
Janus Kinase (JAK) Inhibitors	4 weeks prior to screening until after the follow up visit (Day 112).
P-glycoprotein (Pgp) inhibitors including but not limited to amiodarone, azithromycin, captopril, carvedilol, clarithromycin, conivaptan, cyclosporine, diltiazem, dronedarone, erythromycin, felodipine, itraconazole, ketoconazole, lopinavir, ritonavir, quercetin, quinidine, ranolazine, ticagrelor, verapamil [FDA, 2012].	4 weeks prior to first dose (Day 1) until after the follow up visit (Day 112).
Narrow therapeutic index (NTI) CYP3A4 substrates including but not limited to alfentanil, astemizole, cisapride, cyclosporine, dihydroergotamine, ergotamine, fentanyl, pimozone, quinidine, sirolimus, tacrolimus, terfenadine [FDA, 2012].	4 weeks prior to the first dose (Day 1) until after the follow up visit (Day 112).
Biologic therapies for the treatment of rheumatoid arthritis not limited to anti-TNF biologics or other biologics, rituximab, anakinra, abatacept or tocilizumab.	At any time.

Exposure to more than one anti-TNF biologic therapies for the treatment of RA including but not limited to anti-TNF biologics, infliximab, adalimumab, etanercept, certolizumab and golimumab.
 
Exception: Exposure to a single anti-TNF-biologic for which the subject discontinued for a reason other than primary non-response is permitted.
	
Cannot have been exposed to more than one anti-TNF biologic or be on at any time during the study.
 
In the case of a single anti-TNF biologic for which the subject discontinued for a reason other than primary non-response, the subject must not be on for 8 weeks or 5 half lives (whichever is longer) prior to first dose until after the follow up visit (Day 112).

Live vaccination	Live or attenuated vaccinations are not permitted within 30 days of randomization or plan to receive a vaccination during the study until follow-up visit. If indicated, non-live vaccines (e.g., inactivated influenza vaccines) may be administered

Therapy	Time period
	whilst receiving GSK2982772 based on an assessment of the benefit:risk (e.g., risk of decreased responsiveness). Investigators are expected to follow local and/or national guidelines with respect to vaccinations, including against pneumococcus and influenza, in subjects with RA.

## 7. STUDY ASSESSMENTS AND PROCEDURES

Protocol waivers or exemptions are not allowed with the exception of immediate safety concerns. Therefore, adherence to the study design requirements, including those specified in the Time and Events Table (Section 7.1), are essential and required for study conduct.

Supplementary study conduct information not mandated to be present in this protocol is provided in the SRM and laboratory manual. The SRM will provide the site personnel with administrative and detailed technical information that does not impact subject safety.

This section lists the procedures and parameters of each planned study assessment. The timing of each assessment is listed in the Time and Events Table Section 7.1

- At study visits, the Patient Reported Outcomes (PROs) should be completed prior to any other study assessments.
- The timing and number of planned study assessments, including safety, pharmacokinetic, pharmacodynamic/biomarker or others assessments may be altered during the course of the study based on newly available data (e.g., to obtain data closer to the time of peak concentrations) to ensure appropriate monitoring.
- The change in timing or addition of time points for any planned study assessments must be documented in a Note to File which is approved by the relevant GSK study team member and then archived in the study sponsor and site study files, but this will not constitute a protocol amendment.
- No more than 500 mL of blood will be collected over the duration of the study, including any extra assessments that may be required.
- The Institutional Review Board/Independent Ethics Committee (IRB/IEC) will be informed of any safety issues that require alteration of the safety monitoring scheme or amendment of the Informed Consent Form.

## 7.1. Time and Events Table

Procedures	Screening (-30)	Treatment Period 													Early Withdrawal 	Follow Up (±3) 
		Day 1	Day 8 (±3)	Day 15 (±3)	Day 22 (±3)	Day 29 (±3)	Day 36 (±3)	Day 43 (±3) (week 6)	Day 50 (±3)	Day 57 (±3)	Day 64 (±3)	Day 71 (±3)	Day 78 (±3)	Day 85 (+2) (week 12)		
Site Visit	X	X	X	X		X		X		X		X		X	X	X
Phone call					X		X		X		X		X			
General/Safety Assessments and Procedures																
Informed Consent	X															
Subject Demography	X															
Full medical history 	X															
Inclusion/Exclusion Criteria	X															
Full physical exam 	X													X	X	X
Brief physical exam		X 		X		X		X 		X		X				
Vital signs (BP, HR, RR, temperature)	X	X 	X	X		X		X 		X		X		X	X	X
12-lead ECG	X 	X 	X	X		X		X 		X		X		X	X	X
Concomitant medication review & AE reporting/SAEs 	X-----X															
PROs/Questionnaires/Diaries/Disease Assessments and Procedures																
Columbia Suicide Severity Rating Scale (C-SSRS)	X	X 						X 						X	X	
FACIT-fatigue; RA Symptom and Impact Diary 		X 						X 						X	X	
HAQ-DI; Patient Assessment of joint pain 		X 		X		X		X 		X		X		X	X	
Patient Global Assessment (PtGA) 	X	X 		X		X		X 		X		X		X	X	
Tender (28) & Swollen (28) joint count	X	X 		X		X		X 		X		X		X	X	
Physician Global Assessment (PGA)		X 		X		X		X 		X		X		X	X	
MRI/DCE-MRI 		X 						X 						X 	X 	

Procedures	Screening (-30)	Treatment Period 													Early Withdrawal 	Follow Up (±3) 
		Day 1	Day 8 (±3)	Day 15 (±3)	Day 22 (±3)	Day 29 (±3)	Day 36 (±3)	Day 43 (±3) (week 6)	Day 50 (±3)	Day 57 (±3)	Day 64 (±3)	Day 71 (±3)	Day 78 (±3)	Day 85 (+2) (week 12)		
Study Treatment																
Randomisation		X														
Study medication (three times daily) 		X	-----X													
Dispensing of study medication		X				X				X						
Dispensing of diary cards		X	X	X		X		X		X		X				
Collection and review of diary cards			X	X		X		X		X		X		X	X	
Laboratory (Safety) Assessments and Procedures																
TB, HIV, HepB, Hep C Ab, Anti-CCP, Anti-dsDNA, RF	X															
FSH & estradiol (if applicable)	X															
Serum pregnancy test (WCBP only)	X															
Urine pregnancy test (WCBP only) 		X 	X	X		X		X 		X		X		X	X	X
Haematology, chemistry, urinalysis	X	X 	X	X		X 		X 		X 		X 		X	X	X
CRP	X	X 		X		X		X 		X		X		X	X	
Blood sample for PD inflammatory biomarkers, mRNA, and TE 		X 						X 						X	X	
PK blood samples GSK2982772 		X	X 					X 						X	X	
PK blood samples for MTX 		X 	X 					X 								
Pharmacogenetic sample (PGx)		X 														
Synovial biopsies for PK, inflammatory biomarkers, mRNA, target engagement & pathway engagement analysis 		X 						X 							X 	

**Footnotes:**

1. Full medical history (includes past and current conditions, medication history, substance usage, and family history of premature CV disease).
2. Full physical exam (includes height/weight at screening, height not measured at later time points).
3. Triplicate ECG to be performed at screening only.
4. Pre-dose.
5. Any SAEs assessed as related to study participation (e.g., protocol-mandated procedures, invasive tests, or change in existing therapy) or related to a GSK product will be recorded from the time a subject consents to participate in the study up to and including any follow-up. AEs will be collected from the start of Study Treatment until the follow-up contact. On Days 22, 36, 50, 64, and 78, subjects will be questioned about their general health status via phone call.
6. All PRO assessments should be conducted on site before any tests, procedures, or assessments, to avoid influencing the subjects' perception.
7. DCE-MRI will be performed on all subjects, provided that sites have DCE-MRI capability and experience (e.g., hardware and software requirements). If sites do not have DCE-MRI capability or experience, a regular MRI will be performed of the affected hand/wrist. If the same joint is used for MRI and synovial biopsy, MRI should be performed before biopsy (if applicable).
8. Subjects must take study medication three times a day approximately 8 hours apart. Exact time of dosing to be recorded in diary cards. On Day 1, the first study dose will be administered at the site. On Days 8, 43 and 85 only, subjects must not take their medication at home in the morning. Subjects will complete pre-dose assessments and then will be administered their morning dose of medication at site on Days 8 and 43. On Day 85, subjects are no longer receiving study medication.
9. If urine pregnancy test is positive, a confirmatory serum pregnancy test must be performed.
10. Haematology and chemistry only. No urinalysis required on Days 29, 57 and 71. When clinical laboratory samples are taken on the same day as the MRI, the samples should be taken first prior to the administration of the contrast fluid with MRI. If this is not feasible (i.e. MRI is performed first), it is recommended that a separate IV catheter or straight venipuncture be performed in the *opposite* arm to where the MRI contrast fluid was administered.
11. Blood samples for inflammatory biomarkers, mRNA and target engagement. See laboratory manual for full details on sample collection, handling and shipment.
12. PK blood samples for GSK2982772 will be taken pre-dose on Days 8 and 43. Post-dose serial PK samples will be taken on Days 1, 8 and Day 43 at the following time points: 1, 2, 4, and 6 hours. A trough PK sample will be taken on Day 85 or at Early Withdrawal.
13. Only applicable if subjects are on MTX: PK blood samples for MTX will be taken pre-dose GSK2982772 on Day 1 (MTX alone), on Days 8 and 43 (MTX + GSK2982772). Subjects who are on MTX should ideally take their MTX dose on the same day of the week at approximately the same time of the day throughout the study. In addition, the Day 1, 8 and 43 visits should ideally be on the same day of the week.
14. A PGx blood sample is collected at the baseline visit, after the subject has been randomised and provided informed consent for genetic research. If the sample is not collected at the baseline visit, it can be collected at any time during the study after randomisation.
15. Synovial biopsies are optional.
16. Biopsy (if applicable) and MRI only are required at Early Withdrawal visit if subject withdraws after at least 14 days of treatment and prior to Day 43. If a subject withdraws between Days 43 and 57, an MRI is not required at the Early Withdrawal visit. If a subject withdraws on Day 57 or after, an MRI should be performed at the Early Withdrawal visit. A window allowance of  $\pm 3$  days of Early Withdrawal visit is allowed to perform the MRI.
17. Visit windows during the treatment period are relative to Day 1.
18. If a subject withdraws from the study, every effort will be made for the subject to complete an Early Withdrawal visit prior to the Follow Up visit.
19. Follow-up visit should be completed 28 days ( $\pm 3$  days) after the last dose of study medication.
20. MRI (and if applicable; a biopsy) may be performed during the screening window as an additional visit (if required) up to 7 days before Day 1 to allow sites flexibility in scheduling. The MRI must be completed prior to synovial biopsy (if performed on the same joint). The site should be reasonably confident that the subject has fully qualified for the study (e.g., screening clinical labs, vital signs, physical examination, etc.) before the MRI (and if applicable: a biopsy) is/are performed.

21. A biopsy (if applicable) and MRI may be performed on a separate day within the Day 43 window allowance ( $\pm 3$  days). A separate visit to perform the MRI followed by synovial biopsy (if applicable) is only allowed to accommodate scheduling. If biopsy is being performed, this visit must be scheduled after the Day 43 visit where the PK, clinical laboratory tests and other required Day 43 procedures are performed. Subjects must not take their study medication at home in the morning before the full Day 43 visit and also the morning before MRI and biopsy (if applicable) visit if being done on a separate day.
22. For MRI performed on day 85, a visit window of up to 2 days after is allowed in order to perform the MRI.

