## **9.4. Key Elements of Analysis Plan**

### **9.4.1. Primary Analyses**

All safety evaluations will be based on the Safety population. Clinical interpretation will be based on the review and displays of adverse events, clinical laboratory values, vital sign measurements and 12-lead ECG monitoring.

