	
Clinical data: In the FTiH study, no SAEs were reported. One subject experienced an Adverse Effect (AE) herpes zoster approximately 27 days after receiving his last dose with GSK2982772 or placebo. The blinded Investigator determined this to be potentially drug-related.
	
Subject Monitoring:
 
 
• Subjects will be monitored for signs of infection.
 
• See Individual Stopping Criteria for atypical or opportunistic infections (Section 5.4.1).
 

Vaccinations	
There is a theoretical risk that GSK2982772 could decrease an individual's immune response to vaccines or allow symptoms to develop following vaccination with a live vaccine when administered while on therapy.
	
Subject Selection:
 
 
• Attenuated or live vaccines should not be administered to subjects from 30 days prior to the first dose of GSK2982772, during the study and for 5 half-lives plus 30 days (total 32 days) after GSK2982772 is discontinued.
 
• If indicated, non-live vaccines (e.g. inactivated influenza vaccines) may be administered while receiving GSK2982772 based on a treating physician assessment of the benefit:risk (e.g., risk of theoretical decreased responsiveness).
 
• Investigators will be expected to have followed local and/or national guidelines with respect to vaccinations, including against influenza and pneumococcus, in subjects with RA.
 

Respiratory	
Non-clinical data: In the single dose Safety Cardiovascular (CV) and Respiratory Study in monkeys, a decrease in minute volume (MV) and respiratory rate was observed at all doses (10, 100, and 300 mg/kg). These findings were noted to be reversible and mild in severity In a 14-day repeat dose Safety Respiratory Study in monkeys, no respiratory effects on total pulmonary ventilation (minute volume) or respiratory rate were observed at doses of 1 or 10 mg/kg/day. See IB for
	
Subject Monitoring:
 
 
• Subjects should be monitored for standard respiratory-related adverse events.
 
• Vital signs will be monitored during study visits.
 

Potential Risk of Clinical Significance	Summary of Data/Rationale for Risk	Mitigation Strategy

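### No scheduled ECG or vital-sign reading is tied to peak exposure, although the half-life is about 2 hours; setting the untimed Day 8 reading after the site dose would be a cheap improvement

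*Protocol*

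**What the plan says.** Section 9.4.1 of the Protocol bases the primary safety evaluation on "adverse events, clinical laboratory values, vital sign measurements and 12-lead ECG monitoring". Vital signs include respiratory rate.

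In the current Time and Events Table (Section 7.1) the ECG row opens "12-lead ECG X 3 X 4 X X", where the digits are footnote marks. Screening carries footnote 3 (triplicate), Day 1 carries footnote 4 (pre-dose), and Days 8 and 15 carry no mark. Further along the row only Day 43 carries footnote 4. The vital-signs row has the same pattern from Day 1 onward. Sections 7.3.4 and 7.3.5 set posture and rest but no time relative to dose.

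Footnote 8 says "On Days 8, 43 and 85 only, subjects must not take their medication at home in the morning" and then "Subjects will complete pre-dose assessments and then will be administered their morning dose of medication at site on Days 8 and 43". It also states that dosing is over by Day 85 and that the Day 1 dose is given at the site. Footnote 12 says "Post-dose serial PK samples will be taken on Days 1, 8 and Day 43 at the following time points: 1, 2, 4, and 6 hours".

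Section 7 allows assessment times to be changed during the study, for example "to obtain data closer to the time of peak concentrations", through a Note to File.

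The respiratory row of the risk table (Section 4.6.1) reports, for single doses in monkeys, "a decrease in minute volume (MV) and respiratory rate was observed at all doses (10, 100, and 300 mg/kg". The listed mitigation is monitoring for respiratory adverse events and "Vital signs will be monitored during study visits".

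**The concern.** An effect of drug concentration on respiratory rate, blood pressure, heart rate or QTc would be expected mainly around peak. Half-life is short relative to the dosing interval, so concentration swings widely within each interval and the time of a reading decides what it can show. A trough reading is a weak test of such an effect. A set of readings at unknown times after dosing blurs it.

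On Days 1, 8 and 43 the subject is dosed on site and stays for 6 hours of PK sampling. The setting for a reading near peak with a matching concentration already exists, but the table does not use it for two of the four primary safety endpoints.

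**Working it through.** **1. Classify the visits.** The ECG and vital-signs rows of Section 7.1, read with footnotes 4, 8 and 19, give nine visits from Day 1 to follow-up:

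| Timing relative to dose | Visits | Count |
|---|---|---|
| Fixed pre-dose | Day 1 (before any drug), Day 43 | 2 |
| After dosing has ended | Day 85, follow-up | 2 |
| No time set | Days 8, 15, 29, 57, 71 | 5 |
| Set at or near expected peak | none | 0 |

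2 + 2 + 5 = 9. Only Day 43 is both on treatment and fixed in time.

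**2. Day 8.** Both PK rows carry footnote 4 on Day 8, while the ECG and vital-signs cells do not. The table marks pre-dose on Day 8 where it wants it, so those two readings are untimed. Footnote 8 has pre-dose assessments completed before the site dose, so a site could still take them pre-dose. Either way the table does not fix them.

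**3. Size of the trough.** Inputs:
- Half-life about 2 h: Section 4.5 of the original protocol text, repeated in the Amendment 3 change list.
- Dosing interval about 8 h: footnote 8.
- Time of peak (tmax): not stated in the documents. Assumed to be 1 to 2 h after dosing.

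With first-order decline from peak, trough/peak = 2^(−(8 − tmax)/half-life):

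| Half-life | tmax 1 h | tmax 2 h |
|---|---|---|
| 1.5 h | 2^(−7/1.5) = 0.039 | 2^(−6/1.5) = 0.062 |
| 2 h | 2^(−7/2) = 0.088 | 2^(−6/2) = 0.125 |
| 3 h | 2^(−7/3) = 0.198 | 2^(−6/3) = 0.250 |

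At the stated half-life, trough is about 9% to 13% of peak. Over half-lives of 1.5 to 3 h the range is about 4% to 25%. If the Day 43 morning dose is held beyond 8 h, the fraction is lower still.

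**4. Is the half-life coherent?** The Amendment 3 text for Section 4.5 predicts a minimum concentration about 3.5-fold higher on the 8-hourly than on the 12-hourly regimen. The extra 4 h of decline gives a ratio of 2^(4/half-life), ignoring accumulation. For 2 h this is 2^2 = 4.0, or 4.2 with steady-state accumulation. Solving for 3.5 gives a half-life of 4 × ln 2 / ln 3.5 = 2.2 h. The stated value of about 2 h is consistent with this.

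**The case against.** The strongest case against runs as follows.

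- **Near-peak readings are not excluded.** Five of the six on-treatment visits after Day 1 are unrestricted. The home morning dose is withheld only on Days 8, 43 and 85, so Days 15, 29, 57 and 71 may follow a dose. Diary cards hold exact dose times. This stands, and a reader who infers that conclusions would rest mainly on low-exposure readings goes further than the table allows. What remains is that the timing is left to chance. The document shown does not say whether the clock time of each ECG and vital-sign set is recorded.
- **Day 8 can be post-dose.** A reader might take Day 15 as the earliest visit that could fall near peak. Because the Day 8 cells lack footnote 4, that visit is Day 8.
- **Pairing with PK exists.** Day 43 readings pair with the pre-dose sample and Day 85 readings with the trough sample. It would be wrong to infer that pairing is impossible; only a guaranteed pairing near peak is absent.
- **Safety is observed after site dosing.** Adverse events are collected continuously from the start of treatment. The gap concerns the timing of ECG and vital signs, not an absence of safety data.
- **The respiratory signal is limited.** The risk table calls the single-dose monkey findings reversible and mild. It reports no effect in a 14-day monkey study at 1 or 10 mg/kg/day. It also reports no drug-associated respiratory events in 36 healthy men dosed for 14 days with end-tidal CO2, oxygen saturation and nocturnal respiratory-rate monitoring. This stands and limits the weight of the point. Those data do not replace 12-week data in RA patients on background therapy. The risk table shown is the original protocol's; the amended one is not shown.
- **Section 7 already permits re-timing.** It does, and Section 7.3 permits added safety time points. Both are discretionary and schedule nothing.

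**Conclusion.** The point holds as a cheap improvement. No scheduled ECG or vital-sign reading is tied to peak exposure, and the one on-treatment reading with a fixed time is at trough. That follows from the table alone. The size, about 9% to 13% of peak, rests on the stated half-life, an assumed peak at 1 to 2 h and first-order decline; a half-life of 1.5 to 3 h widens it to about 4% to 25%.

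A reader might infer a major safety gap. The documents do not support that: readings near peak can occur at five visits, adverse events are captured throughout, and the reported respiratory data in volunteers and in the repeat-dose monkey study are clean. What is lost is a guaranteed near-peak comparison with concurrent placebo, alongside a measured concentration.

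**What to change.** - Add a footnote to the Day 8 ECG and vital-sign cells in Section 7.1 placing both 1 to 2 h after the site dose, next to the existing 1 h or 2 h PK sample.
- Keep Days 1 and 43 pre-dose. They form a matched pair for change from baseline, which re-timing Day 43 would break.
- Record the clock time of ECG and vital signs on Days 15, 29, 57 and 71, or confirm that the CRF already does so, so that time since dose can be derived from the diary.

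The cost is a footnote and, if not already captured, a time field. There is no added visit, ECG or blood sample, and Section 7 allows the timing change by Note to File. The downside is that any pre-dose Day 8 reading is given up, and Day 8 change from baseline will include a time-of-day difference. The placebo arm shares that difference, so the between-arm comparison is not biased by it, although placebo is small (n=8 in the Section 9.2.1 precision statement) and the comparison will be imprecise.

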### **9.4.3. Other Analyses**

In addition, based on the data that we observe in the study, probabilities of success will be determined, where the definition of success will be dependent on the endpoint. For example, what is the probability that we would observe a certain change in DAS28 (i.e., comparator rate), based on the data that we have observed in the study.

GSK2982772 plasma concentrations will be summarised descriptively by day and nominal sampling time.

Further details regarding the statistical analysis will be outlined in the Reporting and Analysis Plan (RAP).

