
 
• To investigate the effect of 60 mg <del>twice</del> three times daily doses of GSK2982772 on inflammatory biomarkers in synovial tissue from subjects with moderate to severe Rheumatoid Arthritis.
 
	
 
• Change from baseline in CD68+ macrophages, CD55+ fibroblast-like synoviocytes and a number of infiltrating CD3, CD22, CD138 inflammatory cells, and synovial inflammatory biomarkers including, but not limited to VEGF, IL-1<math>\beta</math>, IL-6, TNF<math>\alpha</math>, and MMP-1.
 

 
• To investigate pathway and target engagement following 60 mg <del>twice</del> three times daily doses of GSK2982772 in blood and synovial biopsy tissue in subjects with moderate to severe Rheumatoid Arthritis.
 
	
 
• Pharmacology biomarker endpoints may include, but are not limited to the following, pre-dose at Days 1, 43 (Week 6) and trough on Day 85 (Week 12), as applicable and if evaluable samples and data permit: 
 
• Target Engagement Assay RIP1 (TEAR1) in blood and synovial tissue.
 
• Total or phosphorylated RIP1, MLKL, and RIP3, cleaved and total caspase 3 and caspase 8 signatures in synovial tissue.
 
 
 

 
• To investigate the concentration of
 
	
 
• Pre-dose GSK2982772 synovial tissue
 

Objectives	Endpoints
GSK2982772 and possible drug-related material, as well as specific distribution within tissue if feasible, in the synovial tissue after 60 mg twice three times daily doses of GSK2982772.	biopsies and possible drug-related material concentrations, as well as specific distribution within tissue if feasible, on Day 43 (Week 6), as evaluable samples and data permit.

 
To investigate the effect of 60 mg twice three times daily doses of GSK2982772 on the quality of life of subjects with moderate to severe Rheumatoid Arthritis.
 
	
 
Change from baseline in Health Assessment Questionnaire Disability Index (HAQ-DI).
 
Change from baseline in RA symptom questionnaire score.
 
Change from baseline in Functional Assessment of Chronic Illness Therapy (FACIT)-Fatigue.
 

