#### **Section 4.5 Dose Justification**

The **initial** selection of the 60 mg BID dose ~~to be~~ **being** tested in this study is based on the safety, PK, and PD data from the First Time in Human (FTiH) study, 200975. GSK2982772 administered at 60 mg BID for 14 days was well tolerated and no safety concerns were identified. A BID dosing regimen was **initially** selected over a QD dosing regimen due to the short half-life of GSK2982772 in humans (~2h). Based on preliminary PK/PD modelling of ex-vivo RIP1 target engagement and GSK2982772 concentrations from the multiple dose ascending part of Study 200975, a 60 mg BID dose **was** predicted to have on average 95% RIP1 target engagement in blood and approximately 90% of subjects will have >90% target engagement in blood at  $C_{min}$  **using a novel in-house ex-vivo PD/target engagement assay based solely on the TNF pathway which is believed to be a key component of the RIP1 pathway.**

**However, based on final PK/PD modelling from the full repeat dose part of the Study 200975 (up to 120 mg BID), a 60 mg BID dose is now predicted to have on average 99% RIP1 target engagement in blood and approximately 90% of subjects will have >85% target engagement at  $C_{min}$ . This is lower than our target of achieving >90% target engagement in at least 90% of subjects at  $C_{min}$ . Therefore, a 60 mg TID cohort is now being proposed.**

**The  $C_{min}$  values at 60 mg TID are predicted to be approximately 3.5 fold higher than for 60 mg BID. Using the final PK/PD, a 60 mg TID dose is predicted to have on average 99% RIP1 target engagement in blood and approximately 90% of subjects will have > 96% target engagement at  $C_{min}$ .** No data are currently available about the distribution of GSK2892772 into the synovium. Based on data in non-steroidal anti-inflammatory drugs (NSAIDs), the synovial fluid concentrations fluctuate to a much lesser extent than those in plasma [Netter, 1989]. Peak drug concentrations are generally lower in synovial fluid but are similar to plasma at later time points. Assuming the same is true for GSK2982772, a 60 mg ~~BID~~**TID** dose should provide similar RIP1 target engagement at the site of action as predicted in blood.

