**Treatment Arms and Duration**

Each subject will participate in the study for approximately 20 weeks. This includes a screening period of up to 30 days, an 84 day (12 week) treatment period, and a 28 day follow-up period after the last dose.

Within 30 days of the screening visit (defined as day of consent signing), subjects who are eligible will enter the treatment period and start treatment (or dosing) on Day 1.

The Follow-up Period is 28 days (4 weeks) long. All visits and assessments are detailed in Section 7.1.

Subjects who have completed screening assessments and are eligible will be randomised in a 2:1 ratio (active to placebo) to one of the following treatments:

GSK2982772 60 mg twice daily (BID)

Placebo twice daily (BID)

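### A Day 85 trough sample drawn one or two days late is protocol-compliant but is no longer a trough, and the nominal-time PK summary would still count it as one

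*Protocol*

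**What the plan says.** Section 7.1, footnote 12, sets the last PK sample: "A trough PK sample will be taken on Day 85 or at Early Withdrawal". It gives no time relative to the last dose. The column for that visit is headed "Day 85 (+2) (week 12"), so the visit may fall on Day 85, 86 or 87.

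Dosing does not run that long. The treatment-duration text describes "an 84 day (12 week) treatment period, and a 28 day follow-up period after the last dose", and footnote 8 states "On Day 85, subjects are no longer receiving study medication". The same footnote also lists Day 85, with Days 8 and 43, among the days on which the morning dose must not be taken at home. On spacing it says "Subjects must take study medication three times a day approximately 8 hours apart". Subjects enrolled before Amendment 3 dosed about 12 hours apart (Section 4.2.2).

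Section 4.5 explains the choice of more than one dose a day as "due to the short half-life of GSK2982772 in humans (~2h"). Section 3 lists trough concentration on Day 85 as a secondary endpoint, and places the exploratory pathway and target-engagement measures "pre-dose at Days 1, 43 (Week 6) and trough on Day 85 (Week 12"). Section 9.4.3 says "GSK2982772 plasma concentrations will be summarised descriptively by day and nominal sampling time".

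**The concern.** The four provisions do not fit together. A visit window suited to joint counts or imaging is harmless when the measurement changes slowly. It is not harmless for the plasma trough of a drug with a half-life of about 2 h once dosing has ended.

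Days 8 and 43 do not have this problem. Their windows are wider (±3 days), but dosing continues and the morning dose is held until after the pre-dose sample, so a shifted visit still yields a trough. At Day 85 a delay runs straight into the off-drug period.

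The sample keeps its trough label, and a summary by day and nominal time pools it with genuine troughs. At stake is the week-12 value of a secondary PK endpoint: a few delayed visits could look like a loss of exposure between Week 6 and Week 12.

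**Working it through.** **Inputs**
- Last dose on Day 84: 84 days counted from Day 1, with no dosing on Day 85 (treatment-duration text; Section 7.1, footnote 8).
- Dosing interval: about 8 h three times daily (footnote 8); about 12 h twice daily (Section 4.2.2).
- Visit window: 0 to +2 days (Section 7.1, column heading).
- Half-life t: about 2 h (Section 4.5).
- Upper bound for t: the vaccination row of Section 4.6.1 equates five half-lives plus 30 days with 32 days. Five half-lives are then at most 2 days, so t ≤ 48/5 = 9.6 h.
- Group size: 16 on active treatment three times daily (Section 9.2.1).

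**Step 1: check the half-life against the plan's own figure.** Section 4.5 (Amendment 3 text) predicts a Cmin about 3.5-fold higher three times daily than twice daily. For one compartment at steady state, Cmin is proportional to 2^(−τ/t) / (1 − 2^(−τ/t)).
- At t = 2 h: τ = 8 gives 0.0625/0.9375 = 0.0667; τ = 12 gives 0.0156/0.9844 = 0.0159; ratio 4.2.
- At t = 2.34 h the ratio is 3.5.

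The stated 3.5 is therefore reproduced by a half-life that rounds to 2 h.

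**Step 2: time since last dose.** Take a Day 85 sample one dosing interval after the last dose, and later samples at the same clock time.
- Three times daily: 8, 32 and 56 h on Days 85, 86 and 87.
- Twice daily: 12, 36 and 60 h.
- Excess over the interval in both cases: 0, 24 and 48 h.

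**Step 3: fraction of the true trough** = 2^(−excess/t).

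| Half-life | Day 85 | Day 86 | Day 87 |
|---|---|---|---|
| 2 h | 100% | 2^(−12) = 0.02% | 2^(−24) = 0.000006% |
| 2.34 h | 100% | 0.08% | 0.00007% |
| 9.6 h | 100% | 18% | 3% |

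**Step 4: effect on an arithmetic mean of 16.** With k late samples at fraction f, the mean falls by (k/16)(1 − f). At t = 2 h, f is effectively zero:
- 1 of 16: 6%
- 2 of 16: 12.5%
- 4 of 16: 25%

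At 9.6 h, one sample a day late still costs (1/16)(1 − 0.18) = 5%. The documents do not say how many visits would be late, so k is an assumption.

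**Step 5: how tight a tolerance must be.** At t = 2 h, a sample 2 h late reads 2^(−1) = 50% of trough, 3 h late reads 2^(−1.5) = 35%, and 4 h late reads 2^(−2) = 25%. The last is a three-times-daily subject sampled 12 h after dosing.

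**The case against.** **The two days are meant for MRI only.** Footnote 22 does give MRI a two-day allowance. But the column heading carried +2 in the original protocol's table, before that footnote existed, and footnote 17 treats such windows as visit windows. On the text, the window covers the whole visit.

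**The intended sample is clear.** The word trough, together with the instruction not to dose at home on the morning of Day 85, points to a sample about one interval after the last dose. That instruction would be unnecessary unless dosing might otherwise continue to the visit. This part stands: the protocol does not say what happens to dosing when the visit slips, so the off-drug interval follows from the 84-day wording but is not beyond doubt.

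**Flagging off-time samples belongs in the analysis plan.** Partly right. Sample times are recorded (Section 7.5.1), as are dose times (footnote 8), and Section 9.4.3 leaves further detail to the RAP. But the window, the unbounded trough and the nominal-time rule are all fixed in the protocol, and no later exclusion recovers a trough that was never drawn.

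**The consequence is modest.** This also stands. PK is descriptive, the study is not powered, and proper pre-dose samples exist on Days 8 and 43. The summary statistic is not named either. A median would move little. A geometric mean would fall by 1 − 2^(−12/16) = 41% for a single quantifiable sample 24 h late at a 2 h half-life.

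**Conclusion.** The point holds for the Day 85 plasma trough. A compliant sample on Day 86 or 87 reads about 0.02% or less of the true trough at a 2 h half-life, and at most 18% and 3% at 9.6 h. Each one lowers an arithmetic mean of 16 by about 6%. This rests on dosing ending on Day 84, single-exponential decline, and an assumed number of late visits. It is worth correcting, but it touches a descriptive secondary endpoint and not the primary safety objective.

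Four stronger inferences are not supported:
- **That the week-12 troughs are false lows in general.** Only late samples are; a draw on the morning of Day 85 is valid.
- **That Early Withdrawal samples distort week 12.** Their timing is bounded only by the Follow-up visit, but nothing assigns them to Day 85.
- **That any PK/PD relation is biased.** Concentration and engagement are drawn at the same visit, so a late pair may still be a valid point on the curve.
- **That week-12 engagement and mRNA readings collapse in the same way.** The modelling in Section 4.5 links engagement to regimen at Cmin, so late engagement readings may be lower. No half-life is given for engagement or for the mRNA response, so the size cannot be stated.

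**What to change.** - In footnote 12 and in the PK summary rule, define the Day 85 trough by actual time since last dose: about one dosing interval, set separately for the three-times-daily and twice-daily regimens, with a stated tolerance. At a 2 h half-life a 2 h departure halves or doubles the reading, so the tolerance should be chosen with that in view.
- Do not apply the +2 day window to this sample; it can remain for the other assessments.
- Leave samples outside the range, and all Early Withdrawal samples, out of the Day 85 trough summary, and list them by actual time since dose. Label the paired target-engagement and mRNA samples in the same way.
- The sponsor should reconcile the 84-day dosing period with the instruction about the Day 85 morning dose, so that it is clear what applies when the visit is delayed.

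The cost is wording in the footnote and in the analysis plan. The times needed are already collected, and Section 7 allows assessment timing to be changed by a Note to File without a protocol amendment. The downside is that some week-12 samples leave the trough summary.
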